1.1 Title

Once-Yearly Zoledronic Acid for Treatment of Postmenopausal Osteoporosis (HORIZON - Pivotal Fracture Trial, PFT)

1.2 Intended aim(s)

To assess the effects of 15-minutes annual infusions of zoledronic acid (5mg) on hip fracture risk in postmenopausal women with osteoporosis during a 3-year period.

1.3 Primary endpoint for replication

Co-primary endpoints were incidence of hip fracture and incidence of vertebral fracture. We focus on the risk of hip fracture for replication.

1.4 Required power for primary endpoint and noninferiority margin (if applicable)

Assuming a 3-year fracture rate of 1.8% in the placebo group, it was determined that with 7,400 patients the log-rank test had a power of 90% (with a two-sided alpha of 0.05) to detect a 50% reduction in hip fractures.

1.5 Secondary endpoint for replication (assay sensitivity) and RCT finding

Non-vertebral fracture

1.6 Trial estimate

Hazard Ratio, HR = 0.59 (95% CI, 0.42 to 0.83) comparing zoledronic-acid group vs. placebo group during a 3-year period (Black et al., 2007).

Note. The follow-up period of the RWE replication is set at 18months. In the trial, the HR comparing zoledronic-acid group vs. placebo group during an 18-month period is estimated to be ~ 0.745 . The HR at 18 months is defined as the ratio between the cumulative incidences of hip fracture events in the zoledronic-acid and placebo groups ($HR = \frac{CI_{ZA}}{CI_{placebo}}$) measured after 18 months of follow-up. The estimates of the cumulative incidences of hip fracture events have been extracted by the Kaplan-Meier curves reported in the trial using a dedicated software (Graph Grabber 2.0.2, Quintessa Ldt).

2. Person responsible for implementation of replication in Action

[name], MPH, implemented the study design in the Aetion Evidence Platform. She is not responsible for the validity of the design and analytic choices. All implementation steps are recorded, and the implementation history is archived in the platform.

3. Data Source(s)

Optum CDM, IBM® MarketScan®

4. Study Design Diagram

The study design diagram visualizes key aspects of the longitudinal study design for expedited review.

Cohort Entry Date (Day 1) [Dispensation of Zoledronic acid (5 mg, IV administered annually)] OR [Raloxifene (oral tablet administered daily)] INCL: Diagnosis of Osteoporosis Days [Enrollment, 0] **INCL**: Use of meds for osteoporosis INCL: Age ≥ 65 Days [0] EXCL: Amputation or absence of lower limb Days [Enrollment, 0] EXCL: Prior use of Bisphosphonate OR parathyroid hormon Days [-730, 0] EXCL: Treatment and Prevention of Glucocorticoid-Induced Osteoporosis Days [-730, 0] EXCL: Treatment of Paget's Disease of Bone Days [-730, 0] Days [-450, 0] EXCL: Life expectancy less than 6 months (CCl ≥ 10)

Days [-450, 0] EXCL: Malignant neoplasms Days [-365, 0] ons that influence bone metabolism (e.g frome, Anorexia, bulimia, RA, SLE, IBD, hyperthyroidism, etc.) Days [-365, 0] EXCL: conditions/circumstances likely to lead to poor treatment adherence (Alcohol/drug abuse)

Days [-365, 0] or GH Days [-180, 0] EXCL: End-Stage Liver Disease Days [-180, 0] EXCL: End-Stage Renal Disea Days [-180, 0] Days [-180, 0] EXCL: Pregnancy Days [-180, 0] EXCL: Prior use of oral corticosteroids Days [-30, 0] PRIMARY OUTCOME: Hip fractures Covariate Assessment Window Days [-450, 0] Follow Up Window Days [1, censor^a] ^a Censoring criteria: Day 0 Occurrence of outcome Death Disenrollment Nursing home admission Specific date reached End of index exposure

Figure 1. Design Diagram - HORIZON-PFT TRIAL REPLICATION

5. Cohort Identification

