6.3.2 Study follow-up

Intention-to-treat (ITT) analysis will be conducted with treatment defined as the index drug on day of cohort entry. Because the exposure (zoledronic acid) is administered annually, patients receiving the exposure are automatically covered with medication for at least 12 months. In addition, the comparator (raloxifene) is intended to proxy for placebo, so nonadherence to the comparator does not result in meaningful exposure misclassification. Therefore, the ITT analysis with a follow-up of 18 months (540 days) will be the primary analysis.

The follow-up will start the day after drug initiation (i.e., cohort entry date), as described in the HORIZON-PFT, and will continue until the earliest date of the following events:

- The first occurrence of the outcome of interest,
- The date of end of continuous registration in the database,
- End of the study period,
- Measured death event occurs,
- Nursing home admission
 - Nursing home admissions are considered a censoring event because the data sources utilized typically provide little to no data on a
 patient, particularly on drug utilization, after admission. We will utilize this as an exclusion reason for cohorts for the same
 reason.

7. Initial Feasibility Analysis

Action report name:

For zoledronic acid vs. raloxifene

Optum CDM- https://bwh-dope.aetion.com/projects/details/1406/results/60058/result/0 IBM® MarketScan®- https://bwh-dope.aetion.com/projects/details/1406/results/60058/result/0

Date conducted: 10/17/2020

Complete Action feasibility analysis using age and CCI as the only covariates and the primary endpoint (Section 6.3.1) as the outcome. No measures of association will be computed nor will incidence rates stratified by treatment group.

• Report patient characteristics by treatment group

• For zoledronic acid vs. raloxifene

		Optum CDM		IBM® MarketScan®		
Variable	Raloxifene - Comparator	Zoledronic Acid - Exposure	Difference	Raloxifene - Reference	Zoledronic acid - Exposure	Difference
Number of patients	6,815	6,605	-	6,694	13,997	-
Age						
mean (sd)	73.41 (5.90)	74.02 (5.52)	-0.62 (-0.81, - 0.42)	73.81 (7.06)	75.61 (7.14)	-1.80 (-2.01, - 1.60)
median [IQR]	73.00 [68.00, 78.00]	75.00 [69.00, 79.00]	-	72.00 [68.00, 79.00]	75.00 [70.00, 81.00]	-
Combined Comorbidity Score - CCI (180 days)						
mean (sd)	1.38 (1.52)	1.49 (1.56)	-0.11 (-0.16, - 0.06)	0.96 (1.20)	1.22 (1.35)	-0.27 (-0.30, - 0.23)

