End of index exposure	762 (4.23%)	372 (4.13%)	390 (4.33%)
Maximum follow-up time	11993 (66.52%)	6058 (67.21%)	5935 (65.84%)
End of patient enrollment	4487 (24.89%)	2198 (24.38%)	2289 (25.39%)

• Report follow-up time by treatment group.

Median Follow-Up Time (Days) [IQR] – ITT analysis				
Patient Group Optum CDM IBM® MarketScan®				
Overall Patient Population	540 [404.5, 540]	540 [365, 540]		
Referent - Raloxifene	540 [426, 540]	540 [365, 540]		
Exposure - ZA	540 [386, 540]	540 [364.5, 540]		

• Report overall risk of the primary outcome.

	Optum CDM	IBM® MarketScan®	Pooled
Risk per 1,000 patients	10.9	10.1	10.4

10. Final Power Assessment

Date conducted: 01/19/2021

• Re-calculate power in the appropriate excel table, using the revised number of matched patients from the PS-match in Section 9. All other parameters in the table should be the same as in Section 8.

o Pooled

18,028
9,014
9,014
10.40
0.59
0.05
187.4912
0.950774073

o Optum CDM

Superiority Analysis	
Number of patients matched	6,396
Reference	3,198
Exposed	3,198
Risk per 1,000 patients	10.90
Desired HR from RCT	0.59
Alpha (2-sided)	0.05
Number of events expected	69.7164
Power	0.595938014

o IBM® MarketScan®

O IBIVIO IVIGINOUS CALLO				
Superiority Analysis				
Number of patients matched	11,632			
Reference	5,816			
Exposed	5,816			
Risk per 1,000 patients	10.10			
Desired HR from RCT	0.59			
Alpha (2-sided)	0.05			
Number of events expected	117.4832			
Power	0.815816276			

• Stop analyses until balance and final power assessment are reviewed by primary investigators, FDA, and assigned members of advisory board.

Reviewed by PI:	[name]	Date reviewed:	01/19/21
Reviewed by FDA:	[name]	Date reviewed:	01/19/21
Reasons for stopping			
analysis (if required):			

11. Study Confidence and Concerns

Deadline for voting on study confidence and listing concerns:

Date votes and concerns are summarized:

- If final feasibility and power analyses are reviewed and approved, proceed to the remaining protocol steps.
- All study team and advisory board members that review this protocol should at this stage provide their level of confidence for the success of the RWD study in the Google Form. This form also provides space for reviewers to list any concerns that they feel may contribute to a failure to replicate the findings of the RCT, including differences in study populations, poor measurement of study variables, or residual confounding.

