All responses will be kept confidential and individual-level results will only be shared with the individual respondent.

• After the deadline for voting has passed, provide the distribution of responses and summarize all concerns here.

12. Register study protocol on clinicalTrials.gov

Date conducted:

• Register the study on clinicalTrials.gov and upload this document.

13. Comparative Analyses

Action report name:

Date conducted:

13.1 For primary analysis:

In the PS-matched cohort from Section 9, to estimate the risk of hip fracture for zoledronic acid users versus raloxifene users during an 18-month period using a Cox regression hazard regression model.

13.2For sensitivity analyses:

Secondary analyses:

- In the PS-matched cohort from Section 9, to estimate the risk of non-vertebral fracture for zoledronic acid users versus raloxifene users during an 18-month period using a Cox regression hazard regression model.
- To estimate the risk of hip fracture for zoledronic acid versus non-user comparator using a risk-set sampled cohort.

Subgroup analysis: In the PS-matched cohort from Section 9, to estimate the risk of hip fracture stratified by age (women younger or older than 75 years). The estimates are compared with the results from a post-hoc analysis of the Horizon-PFT on women older than or equal to 75 (Boonen et al.).

14. Requested Results

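### Power is computed at the trial's 3-year HR of 0.59 although the analysis ends at 18 months, where the protocol puts the trial HR at about 0.745; at that value the final pooled power is about 52%, not 95%

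*Protocol*

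**What the plan says.** Section 1.6 reports the trial result as "Hazard Ratio, HR = 0.59 (95% CI, 0.42 to 0.83) comparing zoledronic-acid group vs. placebo group during a 3-year period". Its note then says that the replication has an 18-month follow-up and gives the corresponding trial effect: "In the trial, the HR comparing zoledronic-acid group vs. placebo group during an 18-month period is estimated to be ~ 0.745". That figure comes from the published Kaplan-Meier curves by digitisation: "The HR at 18 months is defined as the ratio between the cumulative incidences of hip fracture events in the zoledronic-acid and placebo groups".

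The 18-month horizon is fixed twice. Section 6.3.2 says: "Therefore, the ITT analysis with a follow-up of 18 months (540 days) will be the primary analysis". Section 13.1 sets the primary analysis "to estimate the risk of hip fracture for zoledronic acid users versus raloxifene users during an 18-month period using a Cox regression hazard regression model".

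The power tables in Section 8 carry the row "Desired HR from RCT 0.59", and so do those in Section 10. Section 10 updates only the number of matched patients: "All other parameters in the table should be the same as in Section 8". The pooled event risk in both sections is 10.4 per 1,000 patients, taken from the feasibility cohort in Section 7, where follow-up was capped at 540 days.

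**The concern.** Power for a time-to-event comparison depends on the number of events and on the log hazard ratio expected over the period in which those events arise. Here the events are counted over 18 months and the hazard ratio is the 3-year one. By the protocol's own account the trial effect was weaker in the first 18 months, so the substitution inflates power in every table.

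Sections 8 and 10 are formal stopping points at which the investigators and the FDA review power, and Section 11 makes continuation depend on that review and approval. The final pooled figure put to them was 95%. The study exists to judge agreement with a randomised trial. A reader who believes power was 95% will tend to take a non-significant result as failed replication or residual confounding, when it may be the expected outcome of too few events. An 18-month estimate set beside 0.59 (0.42 to 0.83) would also look attenuated even if it matched the trial at 18 months.

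**Working it through.** **Inputs**

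- Two-sided alpha 0.05, 1:1 matching (Sections 8 to 10).
- Matched patients and risk per 1,000, final: pooled 18,028 at 10.40; Optum 6,396 at 10.90; MarketScan 11,632 at 10.10 (Section 10).
- Initial: pooled 25,518, Optum 12,130, MarketScan 13,388, at the same risks (Section 8).
- Trial HR: 0.59 over 3 years, about 0.745 at 18 months (Section 1.6).

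**Formula**

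Expected events D = N × risk / 1,000. Schoenfeld power with equal groups = Φ( √(D/4) × |ln HR| − 1.96 ).

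**Step 1: reproduce the stated figure**

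Final pooled: D = 18,028 × 0.0104 = 187.49; √(187.49/4) = 6.846; |ln 0.59| = 0.5276. The product is 3.612; less 1.96 it is 1.652; Φ(1.652) = 0.9508. The protocol states 0.950774. The other five powers also agree to four decimals or within rounding (table below). The Freedman formula would give 0.942, so Schoenfeld is the formula used.

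**Step 2: change only the hazard ratio**

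|ln 0.745| = 0.2944. Final pooled: 6.846 × 0.2944 = 2.015; less 1.96 it is 0.055; Φ(0.055) = 0.522.

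| Table | Events D | Stated power | Recomputed, HR 0.59 | HR 0.745 |
|---|---|---|---|---|
| Section 10 pooled | 187.5 | 0.951 | 0.951 | 0.522 |
| Section 10 Optum | 69.7 | 0.596 | 0.596 | 0.232 |
| Section 10 MarketScan | 117.5 | 0.816 | 0.816 | 0.358 |
| Section 8 pooled | 265.4 | 0.990 | 0.990 | 0.669 |
| Section 8 Optum | 132.2 | 0.858 | 0.858 | 0.395 |
| Section 8 MarketScan | 135.2 | 0.866 | 0.866 | 0.402 |

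Other methods agree for the final pooled table at 0.745: Freedman 0.516, two-proportion test 0.521.

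**Step 3: what the available events can detect**

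With 187.5 events, 80% power requires HR ≤ exp(−(1.96 + 0.8416)/6.846) = 0.664. At HR 0.745, 80% power requires 4 × (1.96 + 0.8416)² / 0.2944² = 362.3, so 363 events. At 10.4 per 1,000 that is 363/0.0104, or about 34,900 matched patients. The whole unmatched cohort is 13,420 + 20,691 = 34,111 patients with 146 + 208 = 354 events, so matching within these data cannot reach 80% at that effect.

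**Step 4: sensitivity to the approximate 0.745**

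Final pooled power is 54.0% at HR 0.740, 50.4% at 0.750, 68.5% at 0.70 and 83.9% at 0.65. Because 0.745 is a ratio of cumulative incidences, it was also converted to a proportional-hazards ratio: at a comparator risk of 1.04%, ln(1 − 0.745 × 0.0104)/ln(1 − 0.0104) = 0.744. The distinction is immaterial.

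**The case against.** The strongest counter-argument concerns the certainty of 0.745. It is read off a printed curve at a single time point, uses only the early events, and comes without a confidence interval. It lies inside the 3-year interval of 0.42 to 0.83, and across that interval the final pooled power runs from over 99% down to about 25%. So 52% is a conditional figure, not the true power. That stands, and the conclusion is worded accordingly. It does not rescue 0.59: the protocol itself offers 0.745 as the trial effect for its chosen window and gives no reason for planning on anything else.

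The label "Desired HR from RCT" is literally true of 0.59, and the calculation is correct for its inputs. This is also fair: the fault is a mismatched planning assumption, not a computing error.

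It can further be said that the data cuts are fixed, so power does not set the sample size. No numeric power threshold is stated, no rule equates p<0.05 with replication, and nothing says the result will be judged against 0.59. Correcting the input changes no eligibility rule, outcome, matching step or model. All of that is so, and it limits the harm to how the study was approved and how its result will be read. Those are the purposes for which the power sections were written.

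**Conclusion.** The concern holds. All six power tables pair a 3-year effect with 18-month events. On the protocol's own 18-month benchmark, final power is about 52% pooled, 23% in Optum and 36% in MarketScan, against the stated 95%, 60% and 82%.

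This rests on two inputs taken from the protocol as they stand: a true hazard ratio of about 0.745, whose uncertainty is not given, and 187.5 pooled events, which applies the overall risk of the unmatched cohort to the matched one. The qualitative conclusion is not sensitive to modest error in the first: 80% pooled power needs a hazard ratio of 0.664 or lower.

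It should be corrected before the comparative results are interpreted, because the stated power is the figure submitted for review and approval.

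**What to change.** - In Sections 8 and 10, recompute power with 0.745 as the planning value and report about 52% pooled, 23% Optum and 36% MarketScan for the final assessment (67%, 39% and 40% for the initial one). Keep the 0.59 figures only as a row labelled as the 3-year reference. Since both sections are dated, reviewed records, add a dated note so that what was originally reviewed remains visible.
- Because 0.745 is approximate, show power over a short range of hazard ratios, for example 0.65 to 0.75.
- In Sections 1.6 and 13.1, name the 18-month estimate as the benchmark for the 18-month analysis. Give an approximate interval if the digitised curves and published counts allow one; otherwise say that none is available.
- State that, at this power, statistical significance alone will not be the criterion for replication.
- Put the revised figures to the investigators and the FDA, who reviewed the originals.

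The cost is one recalculated spreadsheet and some protocol wording. No new patients or data are needed, and the design and analysis are unchanged. The stated power becomes less favourable.

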5.2.1 Eligible cohort entry dates

Zoledronic acid indication for treatment of postmenopausal women with osteoporosis was approved by FDA on Aug 20, 2007.

- IBM® MarketScan®: Aug 21, 2007 December 31, 2018 (end of available data)
- Optum CDM: Aug 21, 2007 Mar 31, 2020 (end of available data)

5.2.2 Specify inclusion/exclusion criteria for cohort entry and define the index date Inclusion and exclusion criteria were adapted from the trial as closely as possible. Definitions for all inclusion/exclusion are provided in **Appendix A** and are summarized in the flowcharts below.

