median [IQR]	1.00 [0.00, 2.00]	1.00 [0.00, 2.00]	-	1.00 [0.00, 1.00]	1.00 [0.00, 2.00]	-

- Report summary parameters of study population FEASIBILITY- FOR STUDY OUTCOME
 For zoledronic acid vs. raloxifene

	Optum CDM	IBM® MarketScan®
Number of patients in full cohort	13,420	20,691
Number of patients dropped as incomplete cases	0	0
Number of patients that did not begin follow-up	0	0
Number of patients in analytic cohort	13,420	20,691
Number of events	146	208
Number of person-years	16,243	24,519
Number of patients in group: Raloxifene - Comparator	6,815	6,694
Number of patients in group: Zoledronic Acid - Exposure	6,605	13,997
Risk per 1,000 patients	10.88	10.05
Rate per 1,000 person-years	-	-

- Report median follow-up time by treatment group
 For zoledronic acid vs. raloxifene

Median Follow-Up Time (Days) [IQR] – ITT analysis					
Patient Group Optum CDM IBM® MarketScan®					
Overall Patient Population	540 [375, 540]	540 [340, 540]			
Referent - Raloxifene	540 [363, 540]	540 [363, 540]			
Exposure - ZA	540 [383, 540]	540 [329, 540]			

- Report reasons for censoring in the overall study population
 For zoledronic acid vs. raloxifene

Reasons	Optum CDM	IBM® MarketScan®
Overall	10750	17260
Outcome	146 (1.1%)	208 (1.0%)
Death	0 (0.0%)	62 (0.3%)
Maximum follow-up time	8,891 (66.3%)	13,112 (63.4%)
End of patient data	0 (0.0%)	0 (0.0%)
End of patient enrollment	2,589 (19.3%)	5,969 (28.8%)
Nursing home Occurred	838 (6.2%)	630 (3.0%)

• Report overall risk of the primary outcome.

	Optum CDM	IBM® MarketScan®	Pooled
Risk per 1,000 patients	10.9	10.1	10.4

8. Initial Power Assessment

Action report name:

For zoledronic acid vs. raloxifene

Optum CDM- https://bwh-dope.aetion.com/projects/details/1406/results/60059/result/0

IBM® MarketScan®- https://bwh-dope.aetion.com/projects/details/1407/results/60061/result/0

Date conducted: 10/17/2020

In order to complete the initial power analysis, the dummy outcome of a 90-day gap in database enrollment will be used. This outcome is used to ensure that no information on the comparative risks of the outcomes of interest are available at this stage. Complete a 1:1 PS-matched comparative analysis using this outcome. PS should include only 2 covariates: age and combined comorbidity index. Power calculations are based on the formulas from Chow et al. (2008).

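### Figure 1 censors at end of index exposure although the primary analysis is ITT, the Section 9 table carries the same label with no nursing-home row, and the nursing-home exclusion in 6.3.2 appears in neither the flowchart nor Appendix A

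*Protocol*

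**What the plan says.** **Censoring.** Section 6.3.2 states that "Intention-to-treat (ITT) analysis will be conducted with treatment defined as the index drug on day of cohort entry" and makes the 18-month (540-day) ITT analysis primary. It argues that stopping the comparator does no harm, because raloxifene stands in for placebo. Follow-up ends at the earliest of outcome, end of registration, end of study period, death or nursing-home admission.

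Figure 1 (Section 4) gives a different list, which closes with "Nursing home admission Specific date reached End of index exposure". Nursing-home admission and end of exposure stand there as two separate reasons.

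The Section 9 table of censoring reasons has five rows: dummy outcome, death, end of index exposure (762; 372 and 390 by arm), maximum follow-up, and end of enrolment. It has no nursing-home row. The follow-up table beside it is headed "Median Follow-Up Time (Days) [IQR] – ITT analysis". The Section 7 censoring table does have a nursing-home row (838 in Optum, 630 in MarketScan) and has no end-of-exposure row. The empty Table 3 in Section 14.3 has two exposure-based rows and none for nursing home.

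**Eligibility.** Of nursing-home admission, 6.3.2 adds: "We will utilize this as an exclusion reason for cohorts". Section 5.2.2 says: "Definitions for all inclusion/exclusion are provided in" Appendix A, with a summary in the flowcharts. Both number their exclusions up to 17, and neither has a nursing-home criterion.

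**The concern.** The censoring rule for the primary analysis is stated in two ways. A programmer who follows Figure 1 would stop follow-up when the index drug stops. That is an on-treatment contrast, not the ITT contrast that 6.3.2 defines and defends. With the Section 9 row as labelled, a reader cannot confirm that the nursing-home rule of 6.3.2 was the one run. Section 9 is also a point at which work stops for review by the investigators and FDA.

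Eligibility is stated in two ways as well. Section 6.3.2 describes a cohort without nursing-home patients, while the counts that feed the match and the power show no such step.

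**Working it through.** **1. Do the Section 9 rows leave room for unlisted nursing-home censorings?**
- Overall: 697 + 89 + 762 + 11,993 + 4,487 = 18,028, the matched N in Section 10.
- Referent: 350 + 36 + 372 + 6,058 + 2,198 = 9,014.
- Exposure: 347 + 53 + 390 + 5,935 + 2,289 = 9,014.

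Every matched woman has a reason. Nursing-home censorings are therefore either absent or counted under another label.

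**2. Does the 762 look like nursing-home censoring?** The Section 7 percentages use the cohort sizes: 838/13,420 = 6.2% and 630/20,691 = 3.0%, as printed. Applied to the matched numbers in Section 10:
- Optum: 838/13,420 × 6,396 = 399.4
- MarketScan: 630/20,691 × 11,632 = 354.2
- Sum: 753.6, or 4.18% of 18,028, against 762 (4.23%) reported.

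The arms are balanced: (390 − 372)/9,014 = 0.20 percentage points, Wald 95% CI −0.39 to 0.79. Maximum follow-up is reached by 67.21% of referent and 65.84% of exposed women, and median follow-up is 540 days in both arms of both databases. None of this suggests on-treatment censoring.

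One limit applies. The Section 7 rows are incomplete:
- Optum: 146 + 0 + 8,891 + 0 + 2,589 + 838 = 12,464 of 13,420, leaving 956 women (7.1%) without a reason.
- MarketScan: 208 + 62 + 13,112 + 0 + 5,969 + 630 = 19,981 of 20,691, leaving 710 (3.4%).
- Neither sum equals the table's own total row, "Overall 10750 17260".

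The agreement of 754 with 762 is therefore strong circumstantial evidence, not proof.

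**3. Do later figures depend on the 762?** Section 9 uses a dummy outcome (a 90-day enrolment gap). The propensity score uses baseline covariates, so the match and the balance do not depend on later censoring. Section 10 takes matched N times overall risk: 18,028 × 10.40/1,000 = 187.49 events. With HR 0.59 and two-sided alpha 0.05, the Schoenfeld formula reproduces the stated power of 0.951 (and 0.596 and 0.816 by database). The 762 do not enter.

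**4. Is a nursing-home exclusion hidden in the flowchart?** Start after the cohort-entry row and subtract the 26 listed steps (4 enrolment and prior-use steps, 3 inclusion, 19 exclusion).

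| | Optum | MarketScan |
|---|---|---|
| After cohort-entry row | 197,572 | 489,107 |
| Enrolment and prior use | −143,377 | −378,854 |
| Inclusion | −27,618 | −69,532 |
| Exclusion | −13,157 | −20,030 |
| Result | 13,420 | 20,691 |

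Both results equal the stated final cohorts, so no unlisted step was applied after the cohort-entry row. The cohort-entry row itself (−77,476,067 and −199,714,801) is not broken down, and the subtraction says nothing about what lies inside it.

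**The case against.** The strongest reply is that the primary rule is not in practical doubt. Section 6.3.2 is the operative text: it gives a closed list and a reason for ignoring discontinuation. Figure 1 is a visual aid, and Section 7, the run with the hip-fracture outcome, has a nursing-home row and no end-of-exposure row. On this view the 762 is a label slip, Table 3 is an unfilled template, and nothing numerical changes.

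Most of this stands. The 762 is very probably a label slip, the shell imposes no rule, and the power figures are untouched. But a slip in Section 9 cannot explain Figure 1, which names both events side by side. The damage to Figure 1 in the available text lies in its exclusion boxes. Its censoring list is readable apart from a stray fragment, and only that list is used here.

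On eligibility, the reply is that the restriction may sit inside the cohort-entry row, and that Appendix A sends readers to an external folder for missing information and full code lists. Both are possible and cannot be checked here. They do not remove the inconsistency: 5.2.2 promises the definitions in Appendix A and the flowcharts, and no criterion row or window appears in either.

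A reader might infer more: that the Section 9 run really was on-treatment, or that nursing-home patients are known to be in the final cohort. The documents support neither. The counts and arm balance point away from the first, and the unbroken cohort-entry row leaves the second open.

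**Conclusion.** Both statements are wrong as written and should be corrected before the comparative analysis, for which Section 13 records no date.

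(1) Figure 1 contradicts 6.3.2 on censoring for the primary analysis. This rests on the text alone and is certain. The Section 9 table carries the same label for 762 women (4.23%) and omits the nursing-home reason that 6.3.2 requires. That these are mislabelled nursing-home censorings is very probable (about 754 expected), assuming that the Section 7 rates carry over to the matched women. No bias in an effect estimate is shown.

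(2) The nursing-home exclusion is stated in 6.3.2 and shown nowhere that 5.2.2 says it should be. It was not applied after the cohort-entry row; whether it was applied within that row cannot be determined. Its effect on cohort size cannot be derived from the protocol.

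**What to change.** **Censoring**
- Remove end of index exposure from the Figure 1 censoring list, so that it matches 6.3.2.
- In Table 3, replace the two exposure-based rows with a nursing-home row, and say whether the row for a specified date means the 540-day end.
- Look up the archived Section 9 run. If the 762 are nursing-home admissions, correct the label. If exposure-based censoring was really applied, correct the setting before the Section 13 analysis and update the Section 9 censoring and follow-up tables.

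The cost is label edits, one lookup and at most one re-run. The match, balance and power stay as they are.

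**Eligibility**
- Reconcile 6.3.2 with the flowchart and Appendix A. If the exclusion is intended, add it with its window and codes, show where it acts in the flowchart, and update the Section 7 to 10 counts, match and power. If it is not intended, delete the sentence.

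Deletion costs one line. Adding a step that has not yet been applied can only shrink the cohort, by an amount not known from the protocol.
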